## 2.4 Section 5.3.4 Prohibited medication

The following medications must not be used during the treatment period (week 0-54):

## 1. Systemically corticosteroids, monoamine oxidase (MAO) inhibitors, systemic non-selective betablockers and growth hormone

*1*. 2. Medications or herbal products that can influence the glucose homeostasis (except for insulin) and/or the immune system. It is up to the investigator to judge which herbal products influence on the glucose homeostasis

## 1. Treatment with any medication for the indication of diabetes or obesity other than insulin and trial medication.

The following medications must not be used during the trial period (week 0-80):

- 1. Live vVaccines with the exception of influenza vaccination according to local diabetes treatment requirements. The influenza vaccine can be given 3 weeks after a dose of NNC0114-0006 and 2 weeks before next dose of NNC0114-0006.
- 2. Systemically corticosteroids, monoamine oxidase (MAO) inhibitors, systemic nonselective beta-blockers and growth hormone unless only prescribed for a short period of time and if determined by investigator not to have an significant extended half-life
- 3. Treatment with any medication for the indication of diabetes or obesity other than insulin and trial medication.

## 2.5 Section 6.3 Exclusion criteria

3. For Poland: Highly effective contraceptive measures are: oral (except low-dose gestagen (lynestrenol and norestisteron)), injectable, or implanted hormonal contraceptives, intrauterine device, intrauterine system (for example, progestin-releasing coil), vasectomized male (with appropriate postvasectomy documentation of the absence of sperm in the ejaculate).

4. For United Kingdom: Male patients who are sexually active *and have partners*-must use a barrier method of contraception (e.g. condom) for the duration of the study.

## 2.6 Section 6.6 Withdrawal criteria

8. Initiation of any prohibited medication (see Section 5.3.4). Use of vaccines in the followup period (week 54 to week 80) is prohibited but will not lead to subject withdrawal.

Protocol Amendment 5		Date:	02 May 2017	Novo Nordisk
Trial ID: NN9828-4150	CONFIDENTIAL	Version:	1.0	
UTN: U1111-1154-7172	CONFIDENTIAL	Status:	Final	
EudraCT No.: 2014-001215-39		Page:	16 of 17	

## 2.7 Section 8.3.2 Self-measured blood glucose

Subjects will be instructed in how to record the results of the self-measured blood glucose (SMBGs) in the e-diaries. The record of each SMPG will include date, time point (e.g. before breakfast, before lunch, etc.) and value. BG should always be measured when a hypo- or hyperglycaemic episode is suspected. Hypoglycaemic and hyperglycaemic episodes will be recorded by the subject in the e-diary (see Section 8.6.3). The investigator may ask the subject to perform additional SMPG measurements if needed for any safety reason.

If subjects have their own CGM or Flash Glucose Monitoring devices they may use these for measuring the 4-point profiles only (i.e. before breakfast, before lunch, before dinner and bedtime) as per section 8.3.3 The use of these devices must be recorded in EDC.

The instruction of use of the CGM and Flash Glucose Monitoring devices is at the discretion of the investigator. These devices will not be supplied nor compensated by Novo Nordisk.

All subjects must receive and be instructed in the use of the blood glucose meter provided by Novo Nordisk. This Novo Nordisk supplied blood glucose meter must be used to:

- confirm any glucose values measured in connection with a hypoglycaemic episode
  - $\circ \leq 3.9 \text{ mmol/l} (70 \text{ mg/dl}) \text{ or}$
  - $\circ$  > 3.9 mmol /l (70 mg/dl) occurring in conjunction with hypoglycaemic symptoms
- confirm any glucose values measured in connection with a hyperglycaemic episode

   > 16.7 mmol/l (300 mg/dl)
- measure all 7-point profiles (all 7 SMPGs from the same device)

## 2.8 Section 8.5.1.1 Glucose metabolism

• C-peptide (non-fasting ) will be measured at Visit 1

## 2.10 Section 8.7 Subject compliance

Throughout the trial, the investigator will remind the subjects to follow the trial procedures and requirements to ensure subject compliance. If a subject is found to be non-compliant, the investigator will remind the subject of the importance of following the instructions given including taking the trial products as prescribed. Substantial failure to comply with the prescribed dose regimen can lead to withdrawal at the discretion of the investigator.

In case of subject non-compliance with data entry in the eDiary, re-training should be performed and documented.

Protocol Amendment no 6 Trial ID: NN9828-4150

CONFIDENTIAL

Date: Version: Status: Page: 17 October 2017 Novo Nordisk 1.0 Final 1 of 3

## **1** Introduction including rationale for the protocol amendment

This amendment was prepared to update protocol NN9828-4150 version 7.0 dated 02 May 2017 with the following change:

• To update contraceptive requirements for subjects in Ireland as per request from the Irish regulatory authority, the Health Products Regulatory Authority on 12 Oct 2017

In this protocol amendment:

- Any new text is written *in italics*.
- Any text deleted from the protocol is written using strike through.

## 2 Changes

## 6.3 Exclusion Criteria

3. For Ireland: Highly effective contraceptive measures are defined as established use of combined oral contraceptives, injected or implanted hormonal methods of contraception, sterilisation, IUD or intrauterine system or true sexual abstinence.

For United Kingdom *and Ireland*: Only highly effective methods of birth control for the duration of the trial are accepted (i.e. one that results in less than 1% per year failure rate when used consistently and correctly). Highly effective contraceptive measures are defined as established use of oral, intravaginal, transdermal combined estrogen and progestogen hormonal methods of contraception; oral, injected or implanted progestogen only hormonal methods of contraception; placement of an intrauterine device or intrauterine hormone releasing system, bilateral tubal occlusion, female sterilisation, vasectomised partner (where partner is sole partner of subject), or true abstinence\*(when in line with preferred and usual lifestyle).

\*Periodic abstinence (e.g., calendar, ovulation, symptothermal, post-ovulation methods), declaration of abstinence for the duration of a trial, and withdrawal are not acceptable methods of contraception.

4. For United Kingdom *and Ireland*: Male patients who are sexually active must use a barrier method of contraception (e.g. condom) for the duration of the study.

CONFIDENTIAL

Date: Version: Status: Page: 23 March 2018 **Novo Nordisk** 1.0 Final 1 of 4

# **1** Introduction including rationale for the protocol amendment

This amendment was prepared to update Protocol NN9828-4150 version 7.0, dated 02 May 2017 with the following changes:

- NN9828-4150 is a 1 year proof of principle trial with 6 months follow-up period. As originally planned, the primary endpoint is at week 54 (visit 63, being last patient last treatment (LPLT)). In addition to the data analysis after last patient last visit (LPLV), Novo Nordisk will introduce an additional database lock (DBL) after visit 63 in order to perform an internal main phase analysis. The DBL will be performed, when all patients have completed the main phase of the trial (treatment period), i.e. after LPLT at visit 63. After the additional DBL, Novo Nordisk will become unblinded, while the trial investigators and patients will remain blinded throughout the entire trial. The objective of the main phase analysis is to inform on future clinical trials. Conduct and design of the ongoing trial will remain unchanged. Following the end of trial, results from the entire trial period (main and extension phase) will be reported.
- To include local Irish Protocol Amendment no 6, dated 17 October 2017, to Protocol version 7.0, dated 02 May 2017. This Amendment contains updates to contraceptive requirements for subjects in Ireland as per request from the Irish regulatory authority, the Health Products Regulatory Authority on 12 October 2017.
- In addition, minor editorial changes are introduced in this amendment.

In this protocol amendment:

- Any new text is written *in italics*.
- Any text deleted from the protocol is written using strike through.

## 2 Changes

### 2.1 List of abbreviations

DBL	Database lock
LPLT	Last patient last treatment
SMBG	self-measured blood glucose

### 2.2 Section 6.3 Exclusion criteria

3. For Ireland: Highly effective contraceptive measures are defined as established use of combined oral contraceptives, injected or implanted hormonal methods of contraception, sterilisation, IUD or intrauterine system or true sexual abstinence.

Protocol Amendment no. 7 Trial ID: NN9828-4150 UTN: U1111-1154-7172 EudraCT no.: 2014-001215-39

CONFIDENTIAL

Date: Version: Status: Page:

For United Kingdom & Ireland: Only highly effective methods of birth control for the duration of the trial are accepted (i.e. one that results in less than 1% per year failure rate when used consistently and correctly). Highly effective contraceptive measures are defined as established use of oral, intravaginal, transdermal combined estrogen and progestogen hormonal methods of contraception; oral, injected or implanted progestogen only hormonal methods of contraception; placement of an intrauterine device or intrauterine hormone releasing system, bilateral tubal occlusion, female sterilisation, vasectomised partner (where partner is sole partner of subject), or true abstinence\*(when in line with preferred and usual lifestyle).

\*Periodic abstinence (e.g., calendar, ovulation, symptothermal, post-ovulation methods), declaration of abstinence for the duration of a trial, and withdrawal are not acceptable methods of contraception.

4. Male of reproductive age who or whose partner(s) is not using highly effective contraceptive methods for the duration of the trial (highly effective contraceptive measures, as required by local regulation or practice, i.e. a measure that results in less than 1% per year failure rate when used consistently and correctly).

**For United Kingdom & Ireland**: Male patients who are sexually active must use a barrier method of contraception (e.g. condom) for the duration of the study.

### 2.3 Section 17.5 Interim analysis

No formal interim analysis has been planned.-*However, an internal Novo Nordisk analysis is to be conducted after global last patient last treatment (LPLT) (visit 63) to inform on future clinical trials. An additional database lock (DBL) will be performed, when all patients have completed the main phase of the trial, i.e. after LPLT at visit 63. After the additional DBL, Novo Nordisk will become unblinded, while the trial investigators and patients will remain blinded throughout the entire trial.* 

NNC0114-0006 Trial ID: NN9828-4150 Clinical Trial Report Appendix 16.1.1

CONFIDENTIAL

Date: Version: Status:

## List of abbreviations

ADA	American Diabetes Association
AE	adverse event
AUC	area under the curve
BG	blood glucose
CI	confidence interval
Cmax	maximum concentration
CPOP	clinical proof of principle
CRF	case report form
CTR	clinical trial report
DBL	Database lock
DKA	diabetic ketoacidosis
DTSQ	Diabetes Treatment Satisfaction Questionnaire
ECG	electrocardiogram
eCRF	electronic case report form
eGFR	estimated glomerular filtration rate
EMA	European Medicines Agency
FAS	full analysis set
FDA	U.S. Food and Drug Administration
FPG	fasting plasma glucose
GAD	glutamic acid decarboxylase
GLP-1	glucagon-like peptide-1
HbA1c	glycosylated haemoglobin
HLA	human leucocyte antigen
IA2	islet antigen-2
IAA	insulin autoantibodies
i.v.	intravenous(ly)
LOCF	last observation carried forward
LPLT	Last patient last treatment
LSMeans	least square mean
mAb	monoclonal antibody
MedDRA	Medical Dictionary for Regulatory Activities
MMRM	mixed model for repeated measurements
MMTT	mixed meal tolerance test
MRT	mean residence time
NK	natural killer
PBMsCs	periphery blood mononuclear cells
PG	plasma glucose
PPG	postprandial glucose
PK	pharmacokinetic

PRO	patient reported outcome
SAE	serious adverse event
SAP	statistical analysis plan
s.c.	subcutaneous(ly)
SD	standard deviation
SE	standard error
SF-36v2	Short Form Health Survey version 2
SLE	systemic lupus erythematosus
SMPG	self-measured plasma glucose
SS	steady state
T1DM	type 1 diabetes mellitus
TSH	Thyroid-stimulating hormone
T-T-T	treat-to-target
ZnT8	zinc-transporter 8

# 1 Introduction

## 1.1 Trial information

This section includes the information of objectives, endpoints and type of trial as described in the trial protocol.

### 1.1.1 Objectives

#### Primary objective

The primary objective is to evaluate the effect of NNC0114-0006, liraglutide, and the combination of NNC0114-0006 and liraglutide, compared to placebo, on preservation of beta-cell function after 54 weeks of treatment in adult subjects with newly diagnosed type 1 diabetes mellitus (T1DM).

#### Secondary objectives

Objectives related to treatment period (from baseline (week 0) to week 54):

- To assess safety and tolerability of NNC0114-0006 and liraglutide in combination and alone in subjects with newly diagnosed T1DM
- To assess effect on glycaemic parameters (including insulin usage and insulin regimen) of NNC0114-0006 and liraglutide in combination and alone in subjects with newly diagnosed T1DM
- To assess pharmacokinetic (PK) properties of NNC0114-0006 and liraglutide in combination and alone in subjects with newly diagnosed T1DM
- To explore biomarkers relevant for the effect of NNC0114-0006 and liraglutide in combination and alone in subjects with newly diagnosed T1DM
- To assess disease burden and health status in subjects with newly diagnosed T1DM treated with NNC0114-0006 and liraglutide in combination and alone

Objectives related to the post-treatment observation period (from week 54 to week 80):

- To assess post-treatment safety and tolerability of NNC0114-0006 and liraglutide in combination and alone in subjects with newly diagnosed T1DM
- To assess post-treatment effect on preservation of beta-cell function of NNC0114-0006 and liraglutide in combination and alone in subjects with newly diagnosed T1DM
- To assess post-treatment effect on glycaemic parameters (including insulin usage and insulin regimen) of NNC0114-0006 and liraglutide in combination and alone in subjects with newly diagnosed T1DM
- To explore biomarkers relevant for the post-treatment effect of NNC0114-0006 and liraglutide in combination and alone in subjects with newly diagnosed T1DM

- To assess post-treatment development of disease burden and health status in subjects with newly diagnosed T1DM treated with NNC0114-0006 and liraglutide in combination and alone

## 1.1.2 Endpoints

### 1.1.2.1 Primary endpoint

The primary endpoint is  $AUC_{0-4h}$  for a mixed meal tolerance test (MMTT) stimulated C-peptide concentration-time curve at week 54 relative to baseline (defined as the MMTT performed at Visit 2).

- $AUC_{0-4h, C-peptide, 54w} / AUC_{0-4h, C-peptide, baseline}$

### 1.1.2.2 Supportive secondary endpoints

#### Supportive secondary efficacy endpoints

- $AUC_{0-4h}$  for MMTT stimulated C-peptide concentration time curve at week 80 relative to baseline\*
- $AUC_{0-2h}$  for MMTT stimulated C-peptide concentration time curve at week 54 and week 80 relative to baseline\*
- Maximum MMTT stimulated C-peptide concentration ( $C_{max, C-peptide}$ ) at week 54 and week 80 relative to baseline\*
- $AUC_{0-4h}$  for MMTT stimulated plasma glucose concentration time curve at week 54 and week 80 relative to baseline
- $AUC_{0-2h}$  for MMTT stimulated plasma glucose concentration time curve at week 54 and week 80 relative to baseline
- Maximum MMTT stimulated plasma glucose concentration ( $C_{max, glucose}$ ) week 54 and week 80 relative to baseline
- Change in total daily insulin dose in units per kg (three day average) from baseline to week 54 and week 80\*
- Change in number of insulin injections per day (three day average) from baseline to week 54 and week 80
- Number of weeks off bolus insulin from baseline to week 54 and week 80
- Change in  $HbA_{1c}$  from baseline to week 54 and week 80\*
- Change in fasting plasma glucose from baseline to week 54 and week 80\*
- Change in fasting C-peptide from baseline to week 54 and week 80\*
- Change in fasting glucagon from baseline to week 54 and week 80
- 7-point self-measured plasma glucose (SMPG) profiles. The following endpoints will be derived:

- 7-point profiles at week 54 and week 80
- Change in postprandial glucose (PPG)/prandial increment (breakfast, lunch, dinner and average over the three meals) from baseline to week 54 and week 80
- Change in mean of 7-point profiles from baseline to week 54 and week 80
- Before breakfast SMPG at week 54 and week 80
- Change in patient reported outcome (PRO) scores (SF36, Experience of Treatment Benefits and Barriers, Diabetes Treatment Satisfaction Questionnaire (DTSQ)) from baseline to week 54 and week 80

\* Key supportive secondary endpoint prospectively selected for disclosure (e.g. clinicaltrials.gov and EudraCT)

### **Supportive secondary safety endpoints**

- Number of treatment emergent adverse events reported
  - from first dose of trial product to week 54
  - from week 54 to week 80
- Number of treatment emergent hyperglycaemic episodes
  - from first dose of trial product to week 54
  - from week 54 to week 80
- Number of treatment emergent episodes of diabetic ketoacidosis (DKA)
  - from first dose of trial product to week 54\*
  - from week 54 to week 80
- Number of subjects experiencing treatment emergent injection/infusion site reactions from first dose of trial product and during treatment period (54 weeks) caused by:
  - NNC0114-0006/liraglutide/placebo injection/infusion
- Number of treatment emergent hypoglycaemic episodes according to the American Diabetes Association (ADA) and Novo Nordisk definitions
  - from first dose of trial product to week 54\*
  - from week 54 to week 80
- Change in body weight from baseline to week 54 and week 80
- Diabetes complications (retinopathy and estimated glomeruli filtration rate) from baseline to week 54 and week 80
- Change in laboratory safety variables (haematology, biochemistry, coagulation, lipids, IgE, urine dipsticks, cytokine panel, and hormones), vital signs, electrocardiograms (ECGs), eye-examination and outcome of physical examination from baseline to week 54 and week 80
- Change in anti-NNC0114-0006 antibodies from baseline to week 54 and week 80
- Change in anti-liraglutide antibodies from baseline to week 54 and week 80

\* Key supportive secondary endpoint prospectively selected for disclosure (e.g. clinicaltrials.gov and EudraCT)

### Supportive secondary biomarker endpoints

- Change in biomarker parameters from baseline to week 54 and week 80
  - Immune phenotyping of peripheral blood mononuclear cells (PBMC) (the analyses will include, but are not restricted to, the following populations):
    - NK subpopulations
    - Monocyte subpopulations
    - CD8+ & CD4+ subpopulations (e.g., anergy/exhaustion vs. activation; memory, effector, regulatory cells; follicular helper (Tfh) & regulatory Tfh)
  - Total IL-21
  - Autoantibodies against glutamic acid decarboxylase 65 (GAD), zinc-transporter 8 (ZnT8), islet antigen-2 (IA2), insulin (IAA)
- Change in serum vitamin D (1,25 dehydroxy-calciferol) from baseline to week 54 and week 80

### Supportive secondary pharmacokinetic endpoints

NNC0114-0006:

- $AUC_{\tau, NNC0114-0006}$ , area under the NNC0114-0006 time-concentration curve over a dosing interval at steady state (SS) (defined as after last dose)
- Terminal half-life ( $t_{1/2}$ ) after last dose of NNC0114-0006
- $V_{ss, NNC0114-0006}$ , the apparent volume of distribution of NNC0114-0006 at steady-state
- $CL_{ss, NNC0114-0006}$ , clearance of NNC0114-0006 at steady state
- $MRT_{, NNC0114-0006}$ , the mean residence time of NNC0114-0006
- $R_{A, AUC, NNC0114-0006}$ , accumulation ratio of NNC0114-0006 defined as  $AUC_{48-54 \text{ weeks}}/AUC_{0-6 \text{ weeks}}$
- $C_{\text{trough}, NNC0114-0006}$ , observed NNC0114-0006 concentration prior to dosing of NNC0114-0006 at steady state
- $C_{1h, NNC0114-0006}$ , observed NNC0114-0006 concentration 1 hour after dosing of NNC0114-0006 at steady state

[figure not shown]
The following pharmacokinetic endpoints for liraglutide will be derived after the last dose administered at week 54:

- $C_{\text{liraglutide}}$ , liraglutide concentration at steady state

#### 1.1.3 Type of trial

The trial is a randomised, multi-centre, multinational, placebo-controlled, double-dummy, double-blind, efficacy, safety and PK CPOP trial in subjects with newly diagnosed T1DM with residual beta-cell function. The trial includes four parallel treatment groups, one with NNC0114-0006 12 mg/kg i.v. every 6 weeks and liraglutide 1.8 mg s.c. daily, one with NNC0114-0006 12 mg/kg i.v. every 6 week, one with liraglutide 1.8 mg subcutaneously (s.c.) daily and, one placebo arm randomised in an even ratio. The randomisation will take place not more than 4 weeks from start of screening (V1). The exposure period for NNC0114-0006 and liraglutide in combination or alone is

54 weeks. The primary endpoint (C-peptide) is at week 54 as defined per U.S. FDA and EMA requirements followed by a 26 weeks observation period. All groups will receive insulin treatment according to a treat-to-target (T-T-T) regimen throughout the entire trial. See Figure 1–1 for the schematic trial design.

**Figure 1–1 Trial design**

## 1.2 Flow-chart

Please refer to the trial protocol, Section 2.

The full PK profile consisting of 25 samples is only applicable for the first minimum 80 subjects. These subjects follow the flowchart listed in the protocol, sub-section 2.1 “Visit procedure for the first 80 randomised subjects only”. The remaining subjects will follow a reduced visit schedule. These subjects follow the flowchart listed in the protocol, sub-section 2.2 “Visit procedure for once 80 subjects have been randomised”.

## 1.3 Scope of the statistical analysis plan

This SAP is based on the protocol “A randomised, double-blind, double-dummy, placebo-controlled, parallel-group multi-centre clinical proof-of-principle trial in adult subjects with newly diagnosed type 1 diabetes mellitus investigating the effect of NNC0114-0006 and liraglutide on preservation of beta-cell function” version 8.0, including amendments no. 1, 2, 3, 4, 5, 6 and 7.

## 2 Statistical considerations

Based on the statistical model, treatment means or geometric means (LSMeans) and treatment comparisons (i.e. treatment differences or treatment ratios) will be presented with 95% confidence intervals (CI) and p-values for the two-sided test of no treatment difference. A significance level of

5% will be used. All pairwise treatment differences (or ratios) will be presented. No adjustment for multiple testing will be performed.

Some endpoints will be summarised for the treatment period, for the observation period and for the entire trial period (i.e. the treatment period together with the observation period)

The treatment period and the observation period will be derived for completed subjects as

- The start of the treatment period will be the date of first trial product administration
- The end of the treatment period will be the date of the visit at week 54 (i.e. the day of visit 63)
- The start of the observation period will be the day after the end of the treatment period
- The end of the observation period will be the date of the last visit

For withdrawn subjects the date of last contact will be the maximum of the date of the last visit and the withdrawal date. The treatment period and the observation period will be derived for withdrawn subjects as

- The start of the treatment period will be defined as described for completed subjects
- The end of the treatment period will be as defined for completed subjects if this date is before or on the date of last contact. Otherwise the end of the treatment period will be the date of last contact
- An observation period will only be defined if the date of last contact is after the end of the treatment period
  - The start of the observation period will be defined as for completed subjects
  - The end of the observation period will be the date of last contact

For endpoints evaluated as change from baseline and/or for baseline adjustment in the statistical analyses, baseline will be defined as the information recorded at the Visit 3 (randomisation). If no measurement is available at Visit 3, then the information recorded at Visit 2 will be used as the baseline. Furthermore, if no measurement is available at Visit 2, then the information recorded at Visit 1 will be used as the baseline.

In case an endpoint is assessed at visits other than baseline, week 6, 12, 18, 24, 30, 36, 42, 48, 54, 65, and 80, values from the other visits will not be included in the mixed model for repeated measurements (MMRM).

As there is no previous experience with NNC0114-0006 in subjects with T1DM, the defined endpoints and analyses may be supplemented with additional endpoints or analyses such that a better evaluation of the effect and safety of NNC0114-0006 can be obtained.

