#### 8.1.7 Withdrawn subjects

If a subject is withdrawn from the trial during the treatment period (week 0-54), the investigator must aim to undertake procedures similar to those for Visit 63 as soon as possible and perform the safety follow up visit (Visit 90)  $15 \pm 1$  weeks after last dose of NNC0114-0006. Subjects will be instructed to use appropriate pregnancy prevention until 15 weeks after last dose of NNC0114-0006. The end-of-trial form must be completed, and final drug accountability must be performed even if the subject is not able to come to the trial site. A withdrawal session must be made in the IV/WRS. The case book must be signed after all queries have been closed.

If a subject is withdrawn from the trial during the observation period (week 55-80), the investigator must aim to undertake procedures similar to those for Visit 89 as soon as possible and the safety follow up visit (Visit 90)  $15 \pm 1$  weeks after last dose of NNC0114-0006. Subjects withdrawn 14 weeks or more after last dose of NNC0114-0006 should not attend Visit 90. The end-of-trial form must be completed. A withdrawal session must be made in the IV/WRS. The case book must be signed after all queries have been closed.

Additional follow-up of subjects due to adverse events (AEs) or pregnancy is described in Section 12.3 and 12.5.

If subjects fails to return for these visits or is unable to do so, every effort should be made by the investigator to contact him/her by phone or by sending appropriate correspondence (i.e., certified letter) that will become part of the investigators' file to record that efforts were made to reach the subject.

Although a subject is not obliged to give his/her reason(s) for withdrawing from a trial, the investigator must make a reasonable effort to ascertain the reason(s), while fully respecting the subject's rights. Where the reasons are obtained, the primary reason for not completing the trial must be specified on the end-of-trial form in the eCRF.

If new information becomes available which the safety committee at Novo Nordisk concludes would compromise the safety of the subjects, the trial will be permanently discontinued. In such cases, the subjects will still need follow-up visits as described above, i.e. at discontinuation and at 15 weeks  $\pm 1$  week after last dosage of NNC0114-0006 dosage for safety reasons.

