**Figure 2–2 ADA classification of hypoglycaemia**

### *Analysis of hypoglycaemic episodes*

The number of treatment emergent hypoglycaemic episodes will be summarised by treatment. Separate summaries will be made for the Novo Nordisk and for the ADA classifications and for nocturnal episodes. The summaries will be made for the treatment period, for the observation period and for the entire trial period.

The total number of treatment emergent severe or BG confirmed symptomatic hypoglycaemic episodes will be analysed using a negative binominal regression model with a log link function, and the logarithm of the exposure time as an offset. The model will include treatment, stratum and sex as factors and age as a covariate. The treatment ratio will be estimated and the corresponding two-sided 95% CI will be calculated. The analysis will be made for the treatment period, for the observation period and for the entire trial period.

The total number of treatment emergent nocturnal severe or BG confirmed symptomatic hypoglycaemic episodes will be analysed using the same model as above. The analysis will be made for the treatment period, for the observation period and for the entire trial period.

To the extent that data allows, additional analyses may be performed for the other classes of hypoglycaemic episodes using the same model as described above.

Sensitivity analyses will be made (for each analysed class of hypoglycaemia) comparing number and individual rates of hypoglycaemic episodes, respectively, using the Wilcoxon-Mann-Whitney method. This will be made for all different pairs of treatments.

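### For subjects withdrawn before week 54, off-drug follow-up is reported as treatment period, with no on-treatment analysis beside it and exposure time left undefined

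*SAP*

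**What the plan says.** **Completers (SAP Section 2).** "The end of the treatment period will be the date of the visit at week 54 (i.e. the day of visit 63"), and "The start of the observation period will be the day after the end of the treatment period". The last liraglutide dose is taken the day before that visit (Protocol 5.3.2) and the last infusion is at week 48 (Protocol 5.3.1). A completer's treatment period therefore closes one day after the last liraglutide dose and six weeks after the last infusion.

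**Withdrawn subjects (SAP Section 2).** "For withdrawn subjects the date of last contact will be the maximum of the date of the last visit and the withdrawal date". Where the completers' end date falls no later than that contact, it is used here too. Where it does not, the rule reads: "Otherwise the end of the treatment period will be the date of last contact". Such a subject has an observation period only when last contact comes later than that end. Nothing in the rule refers to the last dose.

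**Visits after withdrawal (Protocol 8.1.7).** For withdrawal in weeks 0 to 54 the investigator should aim to do Visit 63-type procedures promptly and to "perform the safety follow up visit (Visit 90") at 15 ± 1 weeks after the last infusion. Protocol 18.3 keeps the Visit 90 data for the trial report.

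**Where the periods are used (SAP 2.4.1.2).** Summaries of adverse events, ketoacidosis, hyperglycaemia and hypoglycaemia are split by period. The negative binomial hypoglycaemia models are run per period with "the logarithm of the exposure time as an offset". Neither document defines exposure time separately.

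**Endpoints (SAP 1.1.2.2).** The safety endpoints cover first dose to week 54, and week 54 to week 80.

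Protocol Section 17 has the same rule for withdrawn subjects. SAP Section 3 changes only the completers' end date.

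**The concern.** Measured from the last dose, the two groups are handled differently. Off-drug weeks go to the observation period in completers and to the treatment period in early withdrawals. In the hypoglycaemia models, exposure after dosing has stopped pulls an active-versus-placebo rate ratio towards 1. In the other safety summaries, events after stopping sit beside events on drug with nothing to separate them.

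Unequal withdrawal is foreseeable. Protocol 5.3.2 and 6.6 require withdrawal when the lower liraglutide dose is not tolerated. Protocol 18.1 reports gastrointestinal events in 42% of the liraglutide programme, most often early in treatment. Early withdrawals are the ones to whom the rule applies in full. The arm with the poorest tolerability could therefore have its treatment-period hypoglycaemia rate diluted most.

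**Working it through.** **1. Plan figures.** The plan gives no figure on this point. Protocol 6.1 gives 304 randomised and 240 completing. With four equal arms that is 304/4 = 76 and 240/4 = 60, so 16 withdrawn per arm, or 16/76 = 21.05%. The stated power (80.4% with 60 per arm) reproduces at 80.3% with an unequal-variance t-test and does not depend on the period rule.

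**2. The date rule applied.** Assumptions: no missed infusions, all dosing stops at withdrawal, Visit 90 exactly 15 weeks after the last infusion. All entries are in weeks. Brackets show the result if a withdrawn subject has no Visit 63 date to act as a cap.

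| Last infusion | Withdrawal | Visit 90 | Treatment period ends | Off liraglutide, counted | Beyond 6 weeks after infusion, counted |
|---|---|---|---|---|---|
| 0 | 2 | 15 | 15 | 13 | 9 |
| 18 | 18 | 33 | 33 | 15 | 9 |
| 18 | 20 | 33 | 33 | 13 | 9 |
| 18 | 24 | 33 | 33 | 9 | 9 |
| 24 | 27 | 39 | 39 | 12 | 9 |
| 36 | 38 | 51 | 51 | 13 | 9 |
| 42 | 44 | 57 | 54 (57) | 10 (13) | 6 (9) |
| 48 | 50 | 63 | 54 (63) | 4 (13) | 0 (9) |

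Below the cap, off-liraglutide time counted = 15 − (withdrawal week − last infusion week), which runs from 15 down to 9. Time beyond the infusion interval = 15 − 6 = 9.

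**3. Share of time, cut-off at the later of last liraglutide dose and last infusion plus 6 weeks.** Assumptions: stop at week 27, last infusion at week 24, everyone attends Visit 90. The cut-off is max(27, 24 + 6) = week 30, so weeks 30 to 39 (9 weeks) are off treatment.

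- Per withdrawn subject: 9/39 = 23%.
- Per arm at the planned 21%: 16 × 9 / (60 × 54 + 16 × 39) = 144/3864 = 3.7%.
- Per arm at an assumed 30% (23 of 76): 23 × 9 / (53 × 54 + 23 × 39) = 207/3759 = 5.5%.

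**4. Share of time, all off-liraglutide weeks.** Assumption: withdrawal uniform over weeks 0 to 54, so mean time on drug is 27 weeks.

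- Without a cap, mean off-drug time is 15 − 3 = 12.0 weeks. With a week-54 cap it is (7 × 12 + 9 + 3)/9 = 10.67 weeks.
- Full attendance at Visit 90: 16 × 10.67/(3240 + 16 × 37.67) = 4.4% and 16 × 12/(3240 + 16 × 39) = 5.0%.
- With 25% attending, and last contact at withdrawal for the rest: 16 × 2.67/(3240 + 16 × 29.67) = 1.15% and 16 × 3/(3240 + 16 × 30) = 1.29%.

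**5. Effect on the hypoglycaemia rate ratio.** Let s be the off-drug share of the active arm's treatment-period time, and assume the rate returns to the placebo rate once drug stops. Then observed ratio ≈ true ratio × (1 − s) + s. This is a person-time approximation to the model.

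- Planned equal dropout (s = 0.044 to 0.050): 2.0 becomes 1.96 to 1.95, and 0.5 becomes 0.52.
- 30 of 76 withdrawn on active: s = 30 × 10.67/(46 × 54 + 30 × 37.67) = 0.089 with the cap and 30 × 12/(46 × 54 + 30 × 39) = 0.099 without. Then 2.0 becomes 1.91 to 1.90, and 0.5 becomes 0.54 to 0.55.
- With s = 0.037 from step 3, 2.0 becomes 1.96.

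**The case against.** The strongest reply is that the rule fits the endpoints. They are defined by a planned window from first dose to week 54, and week 33 of a subject withdrawn at week 20 lies inside it. Choosing time on drug instead is a choice of estimand. A reader might infer that the rule is an error and that the off-drug weeks belong in the observation period. The documents do not support that. The observation period is weeks 54 to 80 in the objectives and endpoints, so the move would put pre-week-54 events into it. This part of the reply stands in full.

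Other points also stand:

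- Only hypoglycaemia is given an exposure-adjusted rate. For adverse event, ketoacidosis and hyperglycaemia counts a longer window can only add events.
- Hypoglycaemia is not confined to time on trial product, because insulin continues in every arm afterwards (Protocol 5.4).
- Protocol 8.1.7 asks investigators to aim for the visits and provides for subjects who do not return, so full attendance is an upper case.
- Whole-trial summaries and full adverse event listings are planned, so no event is hidden. SAP Section 2 also allows supplementary analyses.
- If the early-withdrawal visit were recorded as Visit 63, the treatment period might close there and the issue would vanish for those subjects. The SAP ties the end to the week-54 visit, which points the other way, but it does not settle the matter.

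The reply does not supply an on-treatment analysis, a definition of exposure time, or a statement that the period is meant as treatment-policy.

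**Conclusion.** The rule is not wrong as written. It is a planned-window summary that is not labelled as one, and a cheap addition would improve it.

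For subjects withdrawn well before week 54, about 9 weeks beyond the infusion interval and 9 to 15 weeks off liraglutide count as treatment period. With a cut-off at last infusion plus 6 weeks, that is about 23% of such a subject's treatment-period time and 3.7% of an arm's at planned dropout (5.5% at an assumed 30%), if all attend Visit 90. Counting all off-liraglutide time, it is 4.4–5.0% of arm time with full attendance and 1.15–1.29% with a quarter attending. A true hypoglycaemia rate ratio of 2.0 would read about 1.95 at planned equal dropout and about 1.90 with 30 of 76 withdrawn on active. These figures rest on the assumed withdrawal times, and the ratios also on a return to the placebo rate after stopping.

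Two larger readings should be avoided. One could take 12/39 = 31% of a withdrawn subject's time, and 5.0–7.3% of an arm's (16 × 12/3864 and 23 × 12/3759), as the understatement of every drug-related event rate. That counts weeks within six weeks of an infusion as off treatment, although completers' weeks 48 to 54 are treatment time. It also assumes full attendance and applies a rate to events that are only counted. Nor are the same calendar weeks observation time in completers: the contrast holds only as time since last dose.

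The primary endpoint, power and sample size are unaffected.

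**What to change.** In the SAP:

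1. Keep the present periods and state that they are planned-window (treatment-policy) summaries.
2. Define exposure time for the negative binomial offset. State how an early-withdrawal visit with Visit 63-type procedures is dated, and whether the week-54 limit for withdrawn subjects is the planned date.
3. Add an on-treatment version of the hypoglycaemia models and of the adverse event and ketoacidosis summaries. Events and exposure would end at the later of the last liraglutide/placebo dose and the last infusion plus one 6-week interval, and no later than the planned week-54 date. The 6 weeks mirrors how completers are already handled and makes no claim about how long the antibody acts. The double-dummy design lets one rule serve all four arms.
4. Do not move pre-week-54 time into the week 54 to 80 observation period.

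Cost: one more derived date and one more set of tables. Infusion dates are in the eCRF (Protocol 8.6.1) and daily liraglutide/placebo doses in the e-diary (Protocol 8.6.2). SAP 2.3 already uses the last liraglutide dosing date in a sensitivity analysis. An on-treatment comparison has its own selection problem, because it depends on who stops, so it should stand beside the planned-window result and not replace it.
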